5. STUDY PROCEDURES

Pre-Implant

- Patients will be screened for study
- Pre-implant ECG reviewed (to be performed on day of screening)
- Baseline transthoracic echocardiogram (TTE) reviewed (does *not* need to be performed during inpatient hospitalization; outpatient or outside-hospital TTE report may also be performed)
- Patients who screen-in will be provided Kansas City Cardiomyopathy Questionnaire
- NYHA functional class to be determined by treating physician
- Operating physician will be informed of patient allocation to facilitate planning of procedure

Randomization, Implant, and Periprocedure Care

- RA and RV leads will be positioned per routine
 - o Arterial access for CS angiography or LV septal mapping may be performed at the discretion of the implanting physician in order to facilitate optimal lead placement

- 'LV' lead will be positioned in CS or at His-bundle based on allocation assignment
 - o The allocation assignment will be based on randomization schedule (developed using random number generator)
 - o The study coordinator will keep allocations in a sealed envelope and provide to implanting physician at time of procedure
 - o Patients with LBBB and non-LBBB will be randomized separately
 - o Each independent site will maintain their own randomization schedule
- If the initial allocated site is unsuccessful, alternative site will be pursued
- Intracardiac EGM information (surface QRS to LV site or QLV), pacing output, and lead position at final site will be recorded
- Predischarge ECG performed
- Predischarge device interrogation will be performed (as per standard of care)

2-Week Incision Check

- As per routine post-device care, all patients will be scheduled for routine postoperative device check at 2 weeks to evaluate incision
- Device interrogation (as per standard of care)

1-Month Visit

- Routine device interrogation
- Routine clinical check

(Note: Week 2 and Month 1 visits may be combined, per treating doctor discretion, for the simple post-op wound and clinical visit)

3-Month Visit

- Routine ECG
- Routine device interrogation
- Routine clinical check

6-Month Visit

- Post-implant TTE
- Routine ECG
- Routine device interrogation
- Routine clinical check
- Administration of Kansas City Cardiomyopathy Questionnaire
- NYHA functional class to be determined by treating physician

12-Month Visit

- Post-implant TTE
- Routine ECG
- Routine device interrogation
- Routine clinical check

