6. STATISTICAL PLAN AND CONSIDERATIONS

Sample size estimation:

The sample size for this study is a total of 40 subjects (20 HBP and 20 CS lead). The sample size estimate was based on a goal to observe an absolute 10% difference in LVEF between the two groups, leading to a Cohen's d statistic of 1. With a significance level (α) = 0.05 and a power of 0.8, at least 17 subjects will be required in each group. A goal of 40 subjects was made to allow for possible dropout during the study period.

Statistical methods:

Patients will be studied based on the final treatment allocation. Crossovers and reasons for crossover will also be recorded. Fisher's exact or the Chi-Square test will be used for categorical variables, and continuous parameters will be compared by the two-tailed unpaired Student's t test and the F test for analysis of variance (ANOVA), as needed. Kaplan-Meier method will be used for computing the event free survival curves. Each implant strategy will be compared within this cohort of patients for its impact on percent change QRS duration, LVEF, and as clinical outcome. Multiple logistic regression and multiple regressions using the Cox proportional hazards model will be performed to determine the independent association of each of the implant variables with LVEF and clinical outcome.

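### The arm comparison of LVEF and QRS is an unadjusted t test; adding the baseline value as a covariate and the LBBB stratum is a cheap improvement of unknown size

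*Combined protocol and SAP*

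**What the plan says.** Section 6 (Statistical methods) states that "continuous parameters will be compared by the two-tailed unpaired" Student's "t test and the F test for analysis of variance (ANOVA), as needed". It names no factor or covariate for the ANOVA. It continues: "Each implant strategy will be compared within this cohort of patients for its impact on percent change QRS duration, LVEF", followed by clinical outcome. The sample size rests on "a goal to observe an absolute 10% difference in LVEF between the two groups", taken as d = 1, which implies an SD of 10 LVEF points.

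Section 2 (Primary endpoints) defines both the QRS and the LVEF endpoint as change from the pre-implant value. Sections 2 and 5 randomise LBBB and non-LBBB patients separately.

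The baseline data exist. Section 5 (Pre-Implant) has "Baseline transthoracic echocardiogram (TTE) reviewed" and a pre-implant ECG. It accepts an echocardiogram done elsewhere: "outpatient or outside-hospital TTE report may also be performed".

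The only regressions planned are these: "Multiple logistic regression and multiple regressions using the Cox proportional hazards model will be performed". Their stated purpose is to relate implant variables to LVEF and clinical outcome. They do not name baseline or LBBB as covariates in the comparison of arms.

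**The concern.** With 40 patients, precision is the main limit on what the trial can show. Two variables that may explain part of the variation in outcome are already collected. One is used only by subtraction. The other shapes the randomisation and then drops out of the analysis.

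A change score carries all the measurement noise in the baseline reading, including any added by an outside-hospital echocardiogram. A model with baseline as a covariate weights baseline only as far as it predicts follow-up. A t test that ignores a balanced, prognostic stratum remains valid but is conservative. At stake is some power and a narrower confidence interval, not the validity of the result.

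**Working it through.** **The plan's own figure.** Inputs from section 6: two-sided alpha 0.05, difference 10 points, d = 1. For a two-sample t test the noncentrality is d x sqrt(n/2).
- n = 16 per arm: power 0.781.
- n = 17: sqrt(8.5) = 2.915 on 32 df, critical t 2.037, power 0.807.
- n = 20: sqrt(10) = 3.162 on 38 df, critical t 2.024, power 0.869.

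The stated minimum of 17 is reproduced.

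**Assumed inputs.** Two quantities are not in the documents: r, the baseline to follow-up correlation (taken as 0.3, 0.5, 0.7), and k, baseline SD divided by follow-up SD (taken as 0.6 to 1.0). A k below 1 is plausible because eligibility caps LVEF at baseline only.

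**Variance.** With follow-up variance 1, a change score has variance 1 + k² - 2rk. The model with baseline as covariate has residual variance 1 - r². The ratio is

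(1 + k² - 2rk)/(1 - r²) = 1 + (k - r)²/(1 - r²).

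It is never below 1, but the gain vanishes as r approaches k. Example, k = 1, r = 0.3: 1.40/0.91 = 1.54. Example, k = 0.6, r = 0.5: 0.76/0.75 = 1.01.

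**Power if SD 10 is the SD of change.** The comparator is the change-score t test. The model has arm, baseline and LBBB. Values are simulated, include the lost degrees of freedom and chance baseline imbalance, and vary by about a point between runs. Each cell lists r = 0.3 / 0.5 / 0.7.

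| k | variance ratio | model, 17 per arm (t test 0.81) | model, 20 per arm (t test 0.87) |
|---|---|---|---|
| 1.0 | 1.54 / 1.33 / 1.18 | 0.93 / 0.89 / 0.85 | 0.97 / 0.94 / 0.91 |
| 0.8 | 1.27 / 1.12 / 1.02 | 0.88 / 0.84 / 0.80 | 0.93 / 0.89 / 0.87 |
| 0.6 | 1.10 / 1.01 / 1.02 | 0.82 / 0.79 / 0.80 | 0.89 / 0.86 / 0.86 |

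The difference runs from about -2 points (0.79 - 0.81) to +12 (0.93 - 0.81) at 17 per arm, and from -1 (0.86 - 0.87) to +10 (0.97 - 0.87) at 20. If LBBB is not balanced between the groups, the lowest value at 17 per arm is 0.78, a loss of about 3 points.

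**Power if SD 10 is the SD of follow-up LVEF, 17 per arm.** The model has about 0.82-0.83 / 0.89 / 0.97. A change-score t test has 0.66 / 0.81 / 0.95 at k = 1.0 and 0.81 / 0.90 / 0.97 at k = 0.6. The gain is about 16 points at r = 0.3, k = 1.0, and near zero at k = 0.6. A t test on follow-up values alone has 0.81.

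**The LBBB term alone.** Total SD 10, 17 per arm, 50-80% of patients with LBBB (assumed), LBBB balanced; unadjusted against adjusted power:
- strata 2.5 LVEF points apart: 0.81 v 0.81;
- 5 points apart: 0.81 v 0.82-0.83;
- 10 points apart: 0.82-0.84 v 0.87-0.90, where the unadjusted test has type I error of only 0.02-0.03.

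If LBBB is not balanced, the 2.5-point case is 0.81 v 0.80 and the 5-point case 0.81 v 0.81-0.82.

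**Follow-up or change.** Write the model as Y = a + tT + bB + cL + error, with T arm, B baseline and L LBBB stratum. Subtracting B from both sides gives Y - B = a + tT + (b - 1)B + cL + error. The arm coefficient t is the same. This holds for absolute change, not for percent change.

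**The case against.** The strongest reply is that baseline is already used. This stands: section 2 makes both endpoints changes from pre-implant, and section 6 refers to percent change for QRS. A reader might infer from the bare t test that baseline is ignored. The documents do not support that; only its use as a covariate is missing.

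A reader might also infer that the t test is invalid or the sample size wrong. Neither follows. The stated 17 per arm is reproduced, and omitting a balanced stratum makes the test conservative, not liberal.

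The gain is not assured. At k = 0.6, which the entry cap on LVEF makes plausible, it is near zero or slightly negative. The planned 20 per arm already gives 0.87 if few patients drop out. The LBBB term on its own adds little. No figure supports a gain for QRS. All of this stands and limits the point to an optional improvement.

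The planned regressions might be said to cover adjustment already. They do not: they concern implant variables, name no covariates for the arm comparison, and include no linear model for LVEF.

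Finally, the calculations assume groups as randomised, whereas section 6 says "Patients will be studied based on the final treatment allocation". This objection also stands. Crossover can depend on QRS narrowing (section 2), so even LBBB balance between the analysed groups is not guaranteed. An adjusted estimate must not be read as a remedy for that grouping.

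**Conclusion.** The point holds as something to consider, not as an error. The arm comparison of LVEF and QRS is unadjusted: baseline enters only through the change, and the LBBB stratum is unused. For LVEF, under the assumed r and k and with 10 as the SD of change, the effect on power is about -2 to +12 points at 17 per arm and -1 to +10 at 20. If 10 is the SD of follow-up LVEF, the gain over a change score reaches about 16 points at low r and k = 1.0 and is near zero at k = 0.6. The LBBB term alone is worth at most about 2 points unless the strata differ by more than 5 LVEF points. The true gain cannot be stated from the documents, and none is claimed for QRS.

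The choice of primary LVEF visit, what d = 1 refers to, and the missing cut-off for echocardiographic response are separate matters and carry no weight here. The grouping by final treatment is also separate, and larger.

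**What to change.** In section 6 (Statistical methods), state the following:

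- LVEF, in absolute percentage points, is compared by a linear model with treatment arm, baseline LVEF and LBBB stratum.
- QRS duration is compared by the same type of model, with baseline QRS in place of baseline LVEF.
- The adjusted difference and its 95% confidence interval are reported, and the unadjusted t test is kept as a sensitivity analysis.
- No site terms are included. Eight sites would take seven more degrees of freedom, and sites by LBBB gives 8 x 2 = 16 cells for 40 patients.

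The cost is wording only, with no new data or visits. Two degrees of freedom are lost: 32 to 30 at 17 per arm (critical t 2.037 to 2.042) and 38 to 36 at 20 per arm (2.024 to 2.028). If neither covariate helps, the loss is at worst about 1 to 3 points of power. Whether treatment arm means the arm assigned or the treatment finally received must be settled separately.

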DIAGNOSIS AND MAIN INCLUSION CRITERIA	
Patients with heart failure (HF) eligible for CRT as part of routine standard-of-care based on accepted Class I or Class II indications will be considered for this study. Inclusion criteria include:
 
 1) Left ventricular ejection fraction (LVEF) $\leq 35\%$, sinus rhythm (SR), left bundle-branch block (LBBB) morphology, and QRS duration ≥ 150 msec, and NYHA Class II, III, or ambulatory Class IV patients on goal-directed medical therapy (GDMT) [Class I] 2) LVEF $\leq 35\%$, SR with LBBB with QRS 120-149 msec on GDMT [Class IIa] 3) LVEF $\leq 35\%$, SR with non-LBBB with QRS ≥ 150 msec on GDMT [Class IIa] 4) LVEF $\leq 35\%$, in AF if medication or AV nodal ablation will allow near 100% pacing [Class IIa] 5) LVEF $\leq 35\%$ undergoing new or replacement device with anticipated $>40\%$ ventricular pacing on GDMT

	
[Class IIa]
 
6) LVEF $\leq 30\%$, ischemic etiology of HF, SR with LBBB ≥ 150 msec and NYHA Class I symptoms on GDMT [Class IIb]
 
7) LVEF $\leq 35\%$, SR with non-LBBB with QRS 120-149 msec, NYHA Class III/ambulatory Class IV HF on GDMT [Class IIb]
 
8) LVEF $\leq 35\%$, SR with non-LBBB with QRS ≥ 150 msec, NYHA Class II HF on GDMT [Class IIb]

STUDY PRODUCT	
His-Bundle lead placement will require use of Medtronic delivery sheath (C315 HIS, Medtronic, Minneapolis, MN) and pacemaker lead (Select Secure 3830, Medtronic, Minneapolis, MN) for patients randomized to His bundle pacing. These are FDA approved for routine clinical use.
 
Coronary sinus LV leads utilized in the study will be FDA approved leads per the discretion of the implanting physician

DURATION OF ADMINISTRATION	Pacing will be delivered throughout the duration of the study, with goal pacing delivery of 95%, as is the standard-of-care for patients receiving CRT
REFERENCE THERAPY	The reference therapy will be the control group; i.e., those patients assigned to CRT with use of a CRT
STATISTICAL METHODOLOGY	Traditional statistical methods will be employed. The student's T-test will be used for continuous comparisons. Fisher's exact or the Chi-square test will be applied for dichotomous variables. Time to endpoint analysis will be performed using the Kaplan-Meier method.

LIST OF ABBREVIATIONS

ACE-I	ANGIOTENSIN-CONVERTING ENZYME INHIBITOR
AF	ATRIAL FIBRILLATION
ARB	ANGIOTENSIN RECEPTOR BLOCKER
BB	BETA-BLOCKER
CRT	CARDIAC RESYNCHRONIZATION THERAPY
CS	CORONARY SINUS

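### Student's t test on groups formed by final lead loses its 5% level if crossover makes the groups unequal and their variances also differ; naming Welch's test is a cheap safeguard

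*Combined protocol and SAP*

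**What the plan says.** Section 6 (Statistical methods) states that "continuous parameters will be compared by the two-tailed unpaired Student's t test", with an ANOVA F test as needed. The Study Summary repeats the choice: "The student's T-test will be used for continuous comparisons". Neither place names an unequal-variance version, so the usual pooled-variance test is what a reader would run.

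The groups are not those formed by randomization: "Patients will be studied based on the final treatment allocation". Section 2 allows a patient to move from CS to HBP when the CS lead cannot be placed. It allows a move from HBP to CS for lead instability, for pacing output, or when the QRS does not narrow enough. Section 5 says the other site is pursued when the allocated one fails.

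The planned size is "a total of 40 subjects (20 HBP and 20 CS lead"). No crossover rate is stated. The only SD information is a common value, implied by the "absolute 10% difference in LVEF between the two groups, leading to a Cohen's d statistic of 1".

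**The concern.** The pooled test estimates one common variance. With equal group sizes that does little harm even if the variances differ. With unequal sizes the larger group dominates the pooled estimate. The standard error is then too small if the smaller group is the more variable one, and too large if it is the less variable one.

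Grouping by final lead gives up the balance that randomization would roughly supply. LVEF and percent change in QRS duration are both named comparisons in Section 6, and their P values could be miscalibrated in a direction that depends on which group shrinks. A liberal test overstates a difference. A conservative test makes a non-significant result more likely, which matters in a trial whose second hypothesis (Section 1B) is that echocardiographic and clinical outcomes are similar. Choosing the test after seeing the variances would be a data-driven choice, so the plan should settle it now.

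**Working it through.** **The plan's own figure.** A difference of 10 LVEF points with d = 1 implies a common SD of 10/1 = 10 points. "With a significance level (α) = 0.05 and a power of 0.8", the noncentral t calculation gives 16.71, which rounds up to 17 per group. This agrees with "at least 17 subjects will be required in each group". Power is 0.807 at 17 per group and 0.869 at 20. The sample size is correct under its own assumptions and is not at issue here.

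**Why both conditions are needed.** Let the groups have sizes n1, n2 and SDs s1, s2.
- True variance of the mean difference: T = s1²/n1 + s2²/n2.
- Variance the pooled test uses, on average: E = sp²(1/n1 + 1/n2), where sp² = [(n1−1)s1² + (n2−1)s2²]/(n1+n2−2).
- If s1 = s2, then T = E for any split. If n1 = n2, then T = E for any SDs. Only the two departures together separate T from E.

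**Example at 12:28** (assumed: a net shift of 8 patients), with the larger group's SD set to 1.
- Smaller group's SD = 2: T = 4/12 + 1/28 = 0.369; sp² = (11×4 + 27)/38 = 1.868; E = 1.868 × 0.1190 = 0.222; T/E = 1.66. The t statistic is inflated by √1.66 = 1.29.
- Smaller group's SD = 0.5: T = 0.25/12 + 1/28 = 0.0565; sp² = (11×0.25 + 27)/38 = 0.783; E = 0.0932; T/E = 0.61. The t statistic is shrunk by √0.61 = 0.78.

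**Error rates by simulation** (normal data, equal means, nominal two-sided 5%, 100,000 runs per cell). All splits other than 20:20, and all SD ratios, are assumptions. The ratio is the smaller group's SD over the larger group's.

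| Split | SD ratio | Student | Welch |
|---|---|---|---|
| 20:20 | 0.5 to 2 | 4.8% to 5.3% | 4.8% to 5.1% |
| 16:24 | 0.67 / 1.5 | 3.6% / 7.0% | 5.1% / 4.9% |
| 12:28 | 1 | 5.0% | 5.1% |
| 12:28 | 0.67 / 1.5 | 2.4% / 9.4% | 5.0% / 5.1% |
| 12:28 | 0.5 / 2 | 1.4% / 12.8% | 4.9% / 5.1% |
| 10:30 | 0.67 / 1.5 | 1.9% / 10.7% | 5.0% / 5.2% |

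With equal SDs Student's test stays at 5.0% to 5.1% even at 6:34. With milder SD ratios of 0.8 and 1.25 it gives about 4.1% to 5.9% at 16:24 and 3.3% to 7.3% at 12:28.

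**The mechanism the protocol supports: QRS change.** The HBP exit rule in Section 2 can remove poor narrowers, which cuts the HBP group's size and its QRS spread together. As an illustration, take only the 20% narrowing criterion, let every patient who misses it leave, and assume percent change has mean −25 and SD 15. The cut lies at z = (−20 + 25)/15 = 0.333. The fraction staying is Φ(0.333) = 0.631, or 12.6 of 20. With λ = φ(0.333)/Φ(0.333) = 0.598, the remaining SD is √(1 − 0.333×0.598 − 0.598²) = 0.67 of the original. If the CS group keeps the original SD and nobody moves from CS to HBP, this is close to the 12:28 row with ratio 0.67: an error of about 2.4%, below the nominal level.

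**Power cost of Welch at d = 1 with equal SDs** (Student v Welch): 20:20, 0.868 v 0.867; 12:28, 0.807 v 0.786; 10:30, 0.760 v 0.725; 8:32, 0.694 v 0.633; 6:34, 0.597 v 0.501.

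**The case against.** The strongest reply is that the documents give neither ingredient. No crossover rate is stated, moves in the two directions partly offset, and the only SD in the plan is a common one. This stands: every error rate away from 5% above depends on an assumed split and an assumed SD ratio, and under mild assumptions the shift is about a percentage point.

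A reader might infer that unequal group sizes by themselves push the error to 13%. They do not, because with equal SDs the test holds 5% at any split. A reader might also take the hyper-response described in Section 1A as a sign that LVEF varies more under HBP. That passage presents hyper-response as something seen with CRT as well, and reports similar benefit for the two modes in the cited crossover study, so it gives no reason for unequal LVEF spread. The QRS exit rule points to a conservative test, not an inflated one, and it is permissive rather than mandatory. The documents therefore offer no mechanism for the 13% end.

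A further objection is that the imbalance comes mainly from grouping by final lead. In an as-randomized comparison at 20:20 or 17:17, Student's test stays at 4.8% to 5.3% even with a twofold SD difference. Selection can also make the group means differ without any treatment effect, which no choice of t test repairs. Both statements are right. They reduce the weight of this point but do not remove it: any final-lead comparison that is kept would still be better calibrated with Welch's test. Exact balance as randomized is not assured either, since each of eight sites keeps its own schedule, separately for LBBB and non-LBBB, for 40 patients in all.

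**Conclusion.** The point holds in a conditional and modest form. The plan pairs a pooled-variance test with groups whose sizes it does not control, and the test loses its 5% level if the variances differ too. Depending on assumptions the documents do not supply, the error ranges from close to nominal, through about 3.5% to 7.0% (16:24, ratio 1.5), to about 1.4% to 13% (12:28, ratio 2). The best-supported case is QRS change, where the test would be too conservative, about 2.4% at 12:28 with a ratio of 0.67. For LVEF, the endpoint that sizes the trial, the documents give no evidence of unequal spread. These rates describe how well the test compares the two final-lead groups. They are not error rates for the treatment effect, which grouping by final lead can bias separately and by more.

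**What to change.** In the Study Summary (Statistical Methodology) and Section 6 (Statistical methods):
- Name Welch's unequal-variance t test for two-group continuous comparisons.
- Name Welch's ANOVA in place of the F test, which makes the same equal-variance assumption. If a linear model is used, specify HC3 standard errors.
- Report the mean difference with the matching 95% CI; Section 6 plans no intervals at present.

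The cost is a short edit. If variances are in fact equal, the power loss at d = 1 is nil at 20:20, about 2 points at 12:28, 3 to 4 at 10:30, and about 6 to 10 at 8:32 to 6:34. The change does not address the selection bias from analysing by final lead, which needs its own remedy. A primary comparison as randomized would deal with that and would also restore most of the balance that protects the pooled test.

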3. SUBJECT SELECTION AND WITHDRAWAL

Sites:

Subjects selected for study will be recruited from eight sites: The University of Chicago Medical Center (Chicago, IL), the Ronald Reagan UCLA Medical Center (Los Angeles, CA), Northwestern University's Northwestern Memorial Hospital (Chicago, IL), Geisinger Cardiology of the Geisinger Health System (Wilkes-Barre, PA), Indiana University Krannert Institute of Cardiology (Indianapolis, IN), Rush University Medical Center (Chicago, IL), Edward Elmhurst Healthcare Edward Hospital (Naperville, IL), Baptist Health Louisville (Louisville, KY). Each site will function independently but follow the same treatment protocol. Each site will maintain

their own randomization schedule. The data from the UCLA, NWU, Geisinger, IU, Rush, Edward, and Baptist Health sites will be shared with the University of Chicago at study completion for data analysis only.

Baptist Health Louisville has formally requested the University of Chicago IRB to serve as its own IRB. The following individuals from Baptist Health will be engaged the conduct of this study in Louisville with the following roles:

- [name] – Principle Investigator
- [name], APRN – Sub-Investigator
- [name] – Research Coordinator
- [name] – Research Coordinator

All of the study team members at Baptist Health have provided their curricula vitae, as well as confirmation of appropriate human subjects protection training.

Eligibility:

Eligible patients will be similar to those previously enrolled in the large randomized controlled trials which guide current indications for CRT. This includes:

- Patients at least 18 years of age
- LV systolic dysfunction with LVEF $\leq 35\%$
- Evidence of intraventricular conduction delay with QRS duration > 120 msec
- NYHA Class II, III, and ambulatory Class IV heart failure with either ischemic or nonischemic cardiomyopathy and patients with NYHA Class I symptoms and ischemic cardiomyopathy

Inclusion:

Inclusion criteria are identical to those presently accepted by the American Heart Association (AHA)-American College of Cardiology (ACC)-Heart Rhythm Society (HRS) for CRT.²⁸ These include:

- 1) Left ventricular ejection fraction (LVEF) $\leq 35\%$, sinus rhythm (SR), left bundle-branch block (LBBB) morphology, and QRS duration ≥ 150 msec, and NYHA Class II, III, or ambulatory Class IV patients on goal-directed medical therapy (GDMT) [Class I]
- 2) LVEF $\leq 35\%$, SR with LBBB with QRS 120-149 msec on GDMT [Class IIa]

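### Randomisation is stratified by site and by LBBB status, but the Section 6 t test uses neither, so any between-site variation stays in the error and a modest amount of precision is lost

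*Combined protocol and SAP*

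**What the plan says.** Section 3 (Sites) states "Subjects selected for study will be recruited from eight sites" and adds "Each site will function independently but follow the same treatment protocol". Section 5 (Randomization, Implant, and Periprocedure Care) states "Each independent site will maintain their own randomization schedule". Section 2 (Randomization scheme) and Section 5 both have LBBB and non-LBBB patients randomised separately. Data from the other sites go to the University of Chicago for analysis at the end of the study.

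Section 6 (Statistical methods) says "continuous parameters will be compared by the two-tailed unpaired Student's t test", with an ANOVA F test where needed but no factor named for it. The logistic and Cox regressions are described only in terms of implant variables. Neither Section 6 nor the Study Summary names site or LBBB status as a factor, stratum or covariate.

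On size, Section 6 assumes an "absolute 10% difference in LVEF between the two groups, leading to a Cohen's d statistic of 1" and concludes "With a significance level (α) = 0.05 and a power of 0.8, at least 17 subjects will be required in each group". The total is 40, and "A goal of 40 subjects was made to allow for possible dropout during the study period". Patients are analysed by the treatment they finally received, and Section 2 permits crossover in both directions.

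Section 5 says the schedules come from a random number generator. No block size is given, and nothing says that arms are balanced within a site's list.

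**The concern.** An analysis normally reflects the factors used to stratify the randomisation. Here patients are the unit of randomisation, and site and LBBB status are strata. The unpaired t test treats the 40 patients as if they came from one list at one centre.

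Site differences are plausible from the protocol itself. The CS lead and generator are left to the operator (Section 4). Arterial access and septal mapping follow the implanting physician's usual practice (Section 2). The baseline echocardiogram may come from an outside hospital (Section 5). Readers are blinded, but central reading is not described.

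What is at stake is precision in a small trial. Section 1B hypothesises similar outcomes, while Section 6 tests for a difference. Lost precision makes a non-significant result more likely, and such a result could be misread as support for similarity.

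**Working it through.** **Inputs from the documents.** Two-sided alpha 0.05, power 0.80, difference 10 LVEF points with d = 1 (so an implied total SD of 10/1 = 10), 20 per arm, eight sites (Sections 3 and 6). Separate lists by site and LBBB status give up to 8 x 2 = 16 lists, with a mean of 40/8 = 5 patients per site and 40/16 = 2.5 per list.

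**Assumptions, not in the documents.** Site share of total variance (ICC) 0 to 0.3; 70% LBBB; sites equal in size or 12/8/6/4/4/3/2/1; allocation within each list either simple or in permuted blocks of 2 or 4.

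**Step 1: the plan's own figure.** SE = SD x sqrt(2/n), with power from the noncentral t distribution on 2n - 2 df.
- n = 16: power 0.781.
- n = 17: SE = 10 x sqrt(2/17) = 3.43; power 0.807. The stated 17 per group reproduces.
- n = 20: SE = 10 x sqrt(2/20) = 3.16; power 0.869.

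**Step 2: upper bound when arms are exactly balanced within site.** Site effects then cancel from the treatment difference, so the true SE is 3.16 x sqrt(1 - ICC), while the t test still reports about 3.16. A model with all site terms has 40 - 9 = 31 df.

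| ICC | True SE | t test SE / true SE | Power with site in the model |
|---|---|---|---|
| 0 | 3.16 | 1.00 | 0.865 |
| 0.05 | 3.08 | 1.03 | 0.881 |
| 0.10 | 3.00 | 1.05 | 0.898 |
| 0.20 | 2.83 | 1.12 | 0.928 |
| 0.30 | 2.65 | 1.20 | 0.955 |

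The nominal t test power for comparison is 0.869.

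**Step 3: power in simulated trials of 40 patients**, t test against a random site intercept, across simple and blocked lists:

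| ICC | t test | Random site intercept | Gain in power points |
|---|---|---|---|
| 0 | 0.85-0.88 | 0.85-0.88 | about 0 |
| 0.2 | 0.86-0.90 | 0.895-0.93 | 2-5 |
| 0.3 | 0.86-0.92 | 0.92-0.96 | 4-6 |

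The gain is present under simple allocation too (0.86 to 0.90 at ICC 0.2). It also persists with an assumed 30% crossover. These figures quantify the site term. The documents give nothing from which to size the contribution of LBBB status.

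**Step 4: the reported standard error in simulation.**
- Blocked lists: the ratio of reported to true SE is about 1.03-1.07 at ICC 0.1-0.2. At ICC 0.3 it is 1.08 or more, reaching about 1.16-1.18. The t test's type I error falls to about 0.035 at ICC 0.2 and 0.026-0.035 at 0.3.
- Simple allocation: the ratio is about 1.00 and type I error about 0.05 at every ICC.
- Blocked lists, ICC 0.1-0.2, with random crossover from HBP to CS and analysis by final treatment: the ratio is 1.02-1.07 with no crossover, 1.00-1.07 at 25% and 0.96-1.02 at 50% (simulation error about 2%).

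**Step 5: cost of adjusting.** Eight fixed site effects under simple allocation lower power at ICC 0 (0.777 against 0.858) and help only at 0.3 (0.892 against 0.864). The random intercept avoids that loss. Its type I error, using a fixed 31 df, ranged from 0.047 to 0.064.

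**The case against.** The pooled t test is defensible with about five patients per site. Any error it makes here is conservative, and power at 20 per arm is 0.869 against a target of 0.80. The site ICC is unknown. It may be small, because the outcomes are changes from baseline and a constant reading offset at a site cancels out. All of this stands, and it is why the point is of low priority.

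A reader might infer that separate site schedules by themselves make the t test's standard error too large. The documents do not support that. Overstatement requires real site differences and arms balanced within site lists. The reference to separate blocks in Section 2 describes keeping LBBB and non-LBBB apart; it does not state a block size. Balance would in any case hold for assigned arms, whereas Section 6 compares final treatments. With substantial crossover the overstatement shrinks and can vanish.

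The objection does not remove the loss of precision. That loss needs only a real site effect, and it appears under simple or blocked lists and with crossover.

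A random intercept also does not always collapse to the pooled analysis when sites are alike: at ICC 0 the site variance was estimated as exactly zero in only 57-62% of simulated trials. The power cost there was still negligible.

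**Conclusion.** The point holds as a modest loss of precision: about 0 power points at ICC 0, 2-5 at 0.2 and 4-6 at 0.3. The ICC range, LBBB share, site sizes and block sizes behind these figures are assumptions. Overstatement of the t test's SE (about 3-7% at ICC 0.1-0.2, up to about 16-18% at 0.3) is conditional on within-site balance that the documents do not state.

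Two further inferences should be resisted. Ignoring site does not inflate type I error in this design, and it does not make the sample size of 17 per group wrong. Nor is site the unit of randomisation, so this is not a cluster-design error. The analysis by final treatment is a separate issue and probably a larger one.

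**What to change.** In Section 6, compare LVEF change and percent QRS change in a linear mixed model with treatment arm, LBBB status as a fixed effect and a random intercept for site, using a small-sample degrees-of-freedom correction. State that when the site variance is estimated as zero the result is the pooled comparison, adjusted for LBBB status. Avoid eight fixed site terms. State how the site lists are generated, including any block size.

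If a re-randomisation p-value is added as a check, apply it to the arms as randomised, within the actual site-by-LBBB schedules. It is not valid for groups defined by final treatment.

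The cost is a few sentences in Section 6 and a few lines of code, with no new data or patients. The downside is that site variance is poorly estimated from eight sites of about five patients, and type I error can reach about 0.06 without the correction, so the correction should be part of the specification.
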